the BOLD signal as an indication of cerebral activation in response to various tastes (milkshake and tasteless) during two 9.6-minute runs and in response to sucrose and tasteless during two 9.6-minute runs. A run consists of multiple blocks of taste (milkshake or tasteless). One block is a series of 4 - 8 presentations of tastes or tasteless; Each presentation starts with a 0.75 cc delivery of liquid over 2 s followed by 7 s in which to swallow. Each taste block is followed by a rinse (0.75 cc deionized water). Before the start of a new block there is a rest period of 10 seconds. Blocks vary in length between 32 and 80 seconds and the order of blocks is counterbalanced across subjects. This design is modified from prior event-related designs so as to yield a 61% improvement in design efficiency (calculated by FMRIB's software library FSL), which we confirmed to lead to more extensive and more intense BOLD response. The data can be analyzed offline and used for experimental control variables. Next, two 6 minutes resting state runs will be collected. During these runs, participants will be asked to stare at a cross-hair on the screen. Finally, a diffusion tensor imaging (DTI) scan will be obtained over 5 minutes.

5. Participants will be then taken out of the scanner and given one oral dose of either 30 mg of Morphine, or 50 mg of Naltrexone or placebo. 60 minutes later, VS will be collected again and logged in to the VS sheet and participants will undergo another scanning session while receiving milkshake, sucrose or tasteless solutions as described in 3 and while at rest. DTI and structural imaging will not be repeated. Blood pressure and heart rate will be continuously monitored during scanning using the Biopac system. The same procedure will be followed for the same participants in two subsequent visits (Day 4 and Day 5). *The*

Figure 1. Schematic illustration of study design; the order is just one example for one participants; the interventions will be randomized in a double blind protocol.

visits will be scheduled within a period spanning 4 weeks but no two-treatment days will be scheduled less than 48 hours apart. The overall design of the study will follow the illustration in Figure 1. However, the order of the interventions (i.e. Morphine, Naltrexone or placebo) will be randomized. The scanning session after medication administration will last between 45-60 minutes. Participants vital signs and mental

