This MR study is for research purposes only and is not in any way a clinical scan to diagnose diseases for subjects. The scans in this study are not designed for diagnosis. The primary investigator, the lab, the MR technologist, and the Magnetic Resonance Research Center are not qualified to interpret the MR scans and cannot give subjects or their doctor a diagnostic evaluation of the images. If we see something on their scan that might be medically significant, we will ask a radiologist or another physician to review the relevant images. If that person recommends that the subject should seek medical advice, then the primary investigator or consulting physician will contact the subject, talk with them about the situation, and recommend that they seek medical advice as a precautionary measure. At that point, the decision to seek advice or treatment is completely up to the subject and their doctor. If the subject's doctor wants to pursue additional MR images, the research scans from this study will not be available, and new scans that are appropriate for medical diagnosis will need to be done. The researchers for this project, the consulting physician, the Magnetic Resonance Research Center, and Yale University are not responsible for any exam or treatment that the subject receives based on these findings.

Risks associated with the physiological recordings of respiration, heart rate, swallowing and galvanic skin response in the MRI environment.:

There are no known risks associated with these recordings. However, should the subjects feel anxious or uncomfortable with the any aspect of the recordings we will simply acquire the fMRI scan without them.

Risks-associated with the BodPod measurement:

There are no known risks associated with the BodPod measurement. However, some people may feel uncomfortable or anxious in the enclosed chamber of the BodPod. After each of the three 50-second measurements the experimenter will open the door. The experimenter can see the subject at all times in the BodPod and will show you the alarm button inside the BodPod that will interrupt the measurement if they feel anxious.

Risks associated with the physiological recordings in the MRI environment:

There are no known risks associated with these recordings. However, should the subjects feel anxious or uncomfortable with the any aspect of the recordings we will simply acquire the fMRI scan without them.

Risks involved with consumption of stimuli:

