Minimizing risk involved with administration of one oral dose of Morphine and Naltrexone

We will minimize the acute risk of administration of oral 30 mg Morphine or 50 mg of Naltrexone by carefully monitoring vital signs and mental status using neuro-checks every 60 minutes after the administration. In addition, the study physician [name] will always be present during the whole duration of the visit when either of these drugs is administered.

Minimizing risk involved with the questionnaires:

Should a subject meet diagnostic criteria for any psychiatric disorder [name] will refer them for treatment. If a participant appears to be distressed or fatigued during assessments, the assessor will halt the procedure and take a break. The session will only recommence when and if the participant reports feeling capable of continuing

Minimizing risks involved with the mock fMRI scanner

We will attempt to minimize any discomfort associated with the mock fMRI scanner by informing the subject about what to expect prior to participation and explaining to them the equipment, how it works, which parts are replaced for every subject and how we clean any components that are not. Subjects will be instructed to tell the experimenter if they feel any discomfort with the procedure so that the session can be terminated.

Minimizing risks involved with MRI

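### The discomfort opt-out allows a post-dose scan without heart rate recording, which conflicts with the protocol's unqualified promise of continuous monitoring during scanning

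*Combined protocol and SAP*

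**What the plan says.** Section V, item 3 (Research Plan), part A, Day 3, step 5 describes dosing and the scan that follows. After the oral dose, "60 minutes later, VS will be collected again and logged in to the VS sheet", and the participant returns to the scanner. The same step states "Blood pressure and heart rate will be continuously monitored during scanning", names the Biopac system as the equipment, and gives no exception. On duration it says "The scanning session after medication administration will last between 45-60 minutes". The procedure is repeated at two further visits in the randomized arm. Part B applies it to 15 open-label patients given morphine.

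Section V, item 9 (Risks) has a paragraph headed "Risks associated with the physiological recordings of respiration, heart rate, swallowing and galvanic skin response in the MRI environment". After saying that no risks are known, it continues: "However, should the subjects feel anxious or uncomfortable with the any aspect of the recordings we will simply acquire the fMRI scan without them". Shortly afterwards a second heading, "Risks associated with the physiological recordings in the MRI environment", names no signal and repeats the same text.

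Section V, item 10 (Minimizing Risks) says that drug risk is reduced by "carefully monitoring vital signs and mental status using neuro-checks every 60 minutes after the administration", and that the study physician "will always be present during the whole duration of the visit when either of these drugs is administered".

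**The concern.** Heart rate is in both statements. In the dosing step its monitoring is a commitment; in the Risks item it is among the recordings that are dropped if the participant dislikes them. The opt-out is not limited to the pre-dose scan, and the protocol nowhere separates recordings made for research from monitoring done for safety. Staff who follow the Risks item as written could run a scan after morphine with a promised safeguard switched off.

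The protocol treats heart rate as a safety variable elsewhere: Day 3, step 2 cancels the visit if it is below 60 on arrival. The Data and Safety Monitoring Plan (item 11) also declines to class the combination of these drugs with fMRI as minimal risk. A measurement that decides whether a person may be dosed should not become optional once the dose has been taken.

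**Working it through.** No sample size, power or error rate depends on this point. The check compares the two texts and works through the timeline.

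**The two statements side by side**

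| | Dosing step (item 3, Day 3, step 5) | Opt-out (item 9) |
|---|---|---|
| Heart rate | Continuous | Named; may be dropped |
| Blood pressure | Continuous | Not named |
| Respiration, swallowing, skin response | No commitment | Named; may be dropped |
| Exception for post-dose scans | Not needed | None stated |
| Order of precedence | None stated | None stated |

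The only signal that is both promised and expressly droppable is heart rate. Blood pressure would be reached only through the second, generic heading, which may be a duplicate.

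**Timeline if the opt-out is used**

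1. Last stated vital signs before the scan: 60 minutes after the dose (step 5).
2. Scan length: 45-60 minutes (step 5).
3. Scan end, assuming it starts straight after that check: 60 + 45 = 105 to 60 + 60 = 120 minutes after the dose.
4. Next check under the hourly rule of item 10: 120 minutes after the dose.
5. Longest gap with no stated heart rate measurement: 120 − 60 = 60 minutes, of which 45-60 are in the scanner.

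A longer gap is possible on another reading. Step 5 goes on to describe two hourly assessments in the 2 hours after the scan. If the first came a full hour after the scan (assumption), it would fall at 165-180 minutes and the gap would be 105-120 minutes. I use the shorter figure, because item 10's hourly rule, read strictly, caps the gap at about 60 minutes.

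**Frequency of the relevant harm**

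Section VI, A.2 lists bradycardia with morphine at <2% and says that side effects depend on dose and route. Item 9 calls severe bradycardia extremely rare. As a rough ceiling, if all 75 targeted participants (Section VII, item 1) had one morphine scan and the <2% applied to a single dose (assumption), fewer than 75 × 0.02 = 1.5 cases of bradycardia of any severity would be expected. Only those arising in a scan where the recording had been declined would matter here. The protocol gives no refusal rate for the recordings, so I do not estimate that number. The figure of about 1 in 15 for discomfort in the mock scanner (item 9) concerns the simulator session and is not a substitute.

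**The case against.** The strongest reply is that the two statements can be reconciled. Step 5 is the operative procedure, with named equipment. Item 9 only asks whether the recordings themselves carry risk. Its list omits blood pressure and adds signals that step 5 never mentions, which suggests that it means research recordings. Nearby text looks carried over from other studies: item 9 mentions odors and a restricted diet, and the consent section mentions puddings. This is a fair reading and may well be what was intended. It is not written down, however, and item 9 names heart rate.

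A second reply is that the consequence is small, and most of this stands:

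- The 60-minute gap is no longer than the interval between the protocol's own hourly checks.
- Each visit begins with a scan before dosing using the same set-up. An objection to the recordings may therefore surface before any drug is given, provided they are in use during that scan.
- Participants with heart rate below 60 or blood pressure below 90/60 on arrival are excluded.
- The physician is present, staff watch the scan, and there is an intercom and an alarm.

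None of these safeguards measures heart rate in the scanner. The alarm also needs an alert participant, and drowsiness with morphine is listed at 9% to >10%.

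A reader might go further and infer that dosed participants could be scanned with no check for hypotension, respiratory depression or apnea. The documents do not support that. Hypotension is detected by blood pressure, which the opt-out's list does not include. The dosing step promises no respiratory monitoring in the scanner, so the opt-out removes no such promise.

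**Conclusion.** The conflict is real and limited. As written, the protocol both promises continuous heart rate monitoring during the post-dose scan and permits that scan without a heart rate recording. The directly relevant harm is bradycardia. If the opt-out is used, up to about 60 minutes could pass without a stated heart rate measurement. This assumes that the scan starts straight after the 60-minute check and that item 10's hourly rule is followed. Harm needs both a refusal and an event and should be rare.

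The text does not show an intention to scan dosed participants unmonitored; it shows two instructions that cannot both be followed. The point is still worth correcting, because it concerns a stated safeguard after an opioid dose and the correction is one of wording.

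**What to change.** Add to item 9, under both headings, that the opt-out does not apply to the heart rate and blood pressure monitoring of Day 3, step 5 on any post-dose scan. If that monitoring is declined or cannot be maintained, the scan is not started or is stopped, and vital signs are taken outside the scanner. The rule should cover all three treatments, because the randomized arm is blinded and staff cannot single out the morphine visit. Respiration, swallowing and skin response may stay optional, since the dosing step makes no commitment on them.

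The monitoring equipment is already in use, so the direct cost is wording. The scientific cost is an occasional missing post-dose scan. In the randomized arm that leaves an empty treatment cell in the three-level repeated measures ANOVA (item 12), and a complete-case analysis would lose the whole participant. In the open-label arm it loses the only post-drug scan that part B describes. Confirming before dosing that the participant accepts the monitoring would keep such losses few.

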- Upon arrival to the Magnetic Resonance Research Center (MRRC) participants a urine drug test will be obtained as well as Breath alcohol levels will be assessed with the Alcohawk Elite Breathalyzer. If any of these tests are positive the study will be cancelled. Next, vitals signs (VS)(blood pressure, heart rate, respiratory rate, pulse oximetry, and temperature). If the urine drug test is positive for opiates or methadone the study will be cancelled and the subject disqualified for this study.
- Participants with BP < 90/60 and/or heart rate < 60 will be excluded and the study will be cancelled. VS will be logged in to a VS sheet and kept with the participant paper record in our study binders. Mental and neurologic status will be assessed for a baseline using the National Institutes of Health (NIH) Stroke Scale Neurological Assessment flow sheet (see attached form).
- 3. Next 20 ml of blood will be withdrawn. All blood samples will be placed in pre-chilled test tubes, and centrifuged at 4 C and the plasma stored at -70 C until analyzed according to standard procedures in the YCCI Core Laboratory
- 4. Next, participants will be undergo fMRI scanning: fMRI session: Set up is as above for fMRI simulator in fMRI training. Prior to getting the subject into the MR-room all people involved with the study walk through a detector designed to detect metal objects. We will use a Siemens 3T Trio TIM scanner with a 32channel head-coil. A T1-weighted 3D MPRAGE sequence (4 minutes) will be performed to obtain a high-resolution anatomical image and echoplanar imaging will be used to measure

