fMRI Data Analysis: The following measures will be derived from brain data: (1) parameter estimates(PE) for milkshake (MS) minus Tls (tasteless) (MS-Tls) will be defined at the single subject level using general linear model (GLM), implemented in FSL toolbox⁵⁵; whole brain connectivity of Blood Oxygen Level Dependent (BOLD) signal, using both MS runs or resting state runs, will be calculated between each voxel, or region of interest (ROI), and every other voxel in the brain to obtain (2) functional connectivity *FC* of specific ROIs or (3) degree maps (DM). *FC* is a measure of the strength of connectivity between an ROI and the rest of the brain; degree *D* is calculated as the total number of connections above a specific correlation threshold between a voxel and all the other voxels in the brain; we will study *D* over a range of thresholds 0.25 < r < 0.65 ⁵⁶. *DM* identifies brain hubs (with high *D*) and therefore allows between groups comparison in the most densely connected areas ^{57,58}.

The design is a within subject repeated measures design with treatment (Morphine, Naltrexone and Placebo) being the repeated measure and groups (healthy control vs. pain patients) as a factor. We will use repeated measures ANOVA to find differences in brain response (i.e. (*MS-Tls*) or *D* or *FC*) and psychophysical ratings of milkshake. The repeated measures design is a powerful one because it does not suffer from between subject

NCT04342130

variability. According to the preliminary data we expect to see decreased response to MS in opiate treated back pain patients and decreased D and FC.

SECTION VI: RESEARCH INVOLVING DRUGS, BIOLOGICS, RADIOTRACERS, PLACEBOS AND DEVICES

If this section (or one of its parts, A or B) is not applicable, state N/A and delete the rest of the section.

A. DRUGS, BIOLOGICS and RADIOTRACERS

1. **Identification of Drug, Biologic or Radiotracer:** What is (are) the **name(s)** of the drug(s) biologic(s) or radiotracer(s) being used? Identify whether FDA approval has been granted and for what indication(s).

- Morphine has U.S. Food and Drug Administration (USFDA) approval for relief of moderate to severe acute and chronic pain for which use of an opioid analgesic is appropriate.
- Naltrexone has USFDA approval for treatment of alcohol dependence and blockade of the effects of exogenously administered opioids.

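### The crossover analysis assigns no stated role to the pre-dose scan taken at every visit and does not say whether the brain response is the post-dose value or the change

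*Combined protocol and SAP*

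**What the plan says.** Item 12 of Section V is the only statistical section. It defines three brain measures: the milkshake-minus-tasteless parameter estimate (MS-Tls), functional connectivity (FC) and degree (D). It then gives the model: "The design is a within subject repeated measures design with treatment (Morphine, Naltrexone and Placebo) being the repeated measure and groups" (healthy controls against pain patients) as a factor, and "We will use repeated measures ANOVA to find differences in brain response". It names no pre/post factor, baseline covariate or change score.

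The scans are described in Section V, item 3, part A, Day 3. Step 4, before the dose, begins "Next, participants will be undergo fMRI scanning" and measures "the BOLD signal as an indication of cerebral activation in response to various tastes (milkshake and tasteless) during two 9.6-minute runs". It continues: "Next, two 6 minutes resting state runs will be collected". Step 5 gives the dose, and 60 minutes later "participants will undergo another scanning session while receiving milkshake, sucrose or tasteless solutions as described in 3 and while at rest". (The scan is described under step 4, so the reference to 3 reads as a numbering slip.) The only exception is stated: "DTI and structural imaging will not be repeated". The same procedure applies on Days 4 and 5, with treatment order randomised.

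The one sentence that comes near to giving the pre-dose data a purpose is in step 4: "The data can be analyzed offline and used for experimental control variables". It names no scan, variable or model term.

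**The concern.** Each crossover participant should supply three pre-dose and three post-dose values of MS-Tls, FC and D. At least two analyses fit the text of item 12: post-dose values compared between treatments, or post-minus-pre changes compared between treatments. They estimate the same treatment contrasts under randomised order but with different variances, and either may be the less precise.

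Item 12 rests its case for precision on the removal of between-subject variability. Variation from visit to visit within a subject stays in every treatment contrast. The same-visit pre-dose scan is the measurement in the design that can reduce it, and it is already being acquired.

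Morphine against placebo and naltrexone against placebo are the contrasts behind the first stated purpose. If the choice between post-dose and change is made after the data are seen, it also becomes an avoidable analyst's choice on those contrasts.

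**Working it through.** The documents give no power calculation, effect size, standard deviation or pre/post correlation, so there is no figure of the plan's own to reproduce. The check is variance algebra over a range of assumed values.

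**1. Set-up.** Remove the subject mean. Let r be the correlation between pre-dose and post-dose values of the same visit, and k the ratio of pre-dose to post-dose standard deviation, both for the visit-specific part. Set the variance of a treatment contrast from post-dose values alone to 1.

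- Change: 1 + k² − 2rk
- Post-dose adjusted for same-visit pre-dose, common slope: 1 − r²
- Change minus adjusted: (1 + k² − 2rk) − (1 − r²) = (k − r)² ≥ 0

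So with a common slope, adjustment is no less precise than either reading, whatever k is, apart from one degree of freedom. Change is worse than post-dose alone when r < k/2, which is r < 0.40 / 0.50 / 0.625 for k = 0.8 / 1 / 1.25.

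**2. Equal variances (k = 1).** Change becomes 2(1 − r).

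| Assumed r | Post-dose | Change | Adjusted |
|---|---|---|---|
| 0 | 1.00 | 2.00 | 1.00 |
| 0.2 | 1.00 | 1.60 | 0.96 |
| 0.4 | 1.00 | 1.20 | 0.84 |
| 0.6 | 1.00 | 0.80 | 0.64 |

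**3. Unequal slopes.** Suppose r = 0.6 under placebo and naltrexone but m under morphine. The pooled slope is b = (0.6 + 0.6 + m)/3, and the adjusted morphine–placebo variance is 1 + b² − b(0.6 + m).

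- m = 0.2: b = 0.467, variance 0.84
- m = 0: b = 0.400, variance 0.92
- m = −0.2: b = 0.333, variance 0.98

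The gain shrinks but does not reverse in these cases.

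**4. What this means for power, as illustration only.** Assume one scalar outcome, effect 0.3 SD, between-visit correlation 0.5 and two-sided alpha 0.05. Assume also 60 crossover participants, the enrolment target of 75 less the 15 open-label patients; the documents do not say that the 15 are part of the 75. Then SE² = 2(1 − 0.5) × relative variance / n. The degrees of freedom are 2n − 4 = 116 without the covariate and 115 with it, and the adjusted variance is inflated by 1 + 1/(df − 1). The noncentral t gives, at r = 0 / 0.2 / 0.4 / 0.6:

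- n = 60: post-dose 0.635; change 0.371 / 0.445 / 0.557 / 0.731; adjusted 0.631 / 0.649 / 0.707 / 0.818
- n = 30: post-dose 0.365; change 0.208 / 0.248 / 0.314 / 0.439; adjusted 0.360 / 0.372 / 0.415 / 0.516

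The cost of an uninformative covariate (r = 0) is about 0.004 to 0.006 in power.

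**5. Carryover into the covariate.** Suppose morphine shifts the next visit's pre-dose scan by an assumed 0.3 SD and has no effect on that visit's post-dose scan. With six equally likely orders, morphine immediately precedes placebo in two, so the placebo pre-dose mean shifts by 0.3 × 2/6 = 0.10 and the morphine pre-dose mean by 0. With slope 0.6, the adjusted morphine–placebo contrast moves by 0.6 × 0.10 = 0.06, so a true 0.30 is estimated as 0.36 while the unadjusted contrast stays at 0.30. If the shift persists to the post-dose scan, the unadjusted contrast falls to 0.30 − 0.10 = 0.20 and the adjusted one to 0.26. Simulation at n = 60 agrees with all four values to within 0.01.

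**The case against.** The strongest reply is that an unadjusted repeated-measures ANOVA of a randomised crossover is valid, that the design already removes between-subject variance, and that any further gain rests on a correlation nobody has documented. All of that stands. At r = 0 to 0.2 the gain over post-dose alone is negligible. Item 12 also leaves other choices open, such as regions of interest, run type and the D threshold, so this is not its only loose end.

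Two further objections stand and shape the fix. First, adjustment adds an assumption that post-dose analysis does not need: earlier doses must not shift later pre-dose scans. The minimum gap is 48 hours. With the 2–4 hour morphine half-life in the Research Plan, that is at least 48/4 = 12 half-lives, so a large morphine carryover is unlikely; no naltrexone half-life is given. Second, for voxel-wise MS-Tls and D the covariate differs at every voxel and, for D, at every threshold. This is more than a change of wording.

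A reader might infer that the plan discards the pre-dose scans, or that it certainly loses precision. The documents do not support either. The text is compatible with a change analysis, which would use those scans, and without r no loss can be shown. Nor is there a case for bias, because treatment order is randomised.

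**Conclusion.** The point holds as a gap in specification with a cheap improvement attached. Item 12 does not say which scan or scans supply the brain response, and the sentence in step 4 about control variables does not settle it. The open readings are not interchangeable: with equal variances, change has up to twice the variance of post-dose alone at r = 0, equals it at r = 0.5, and is better above that. Adjustment is at least as precise as both under a common slope, with 0% to 36% less variance than post-dose alone for r from 0 to 0.6.

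This rests on assumed r, on a slope that is similar across treatments, and on no material carryover into later pre-dose scans. The gain may be nil, will differ by voxel, region and measure, and the illustrative powers carry over to none of them in particular. It is worth doing, but the trial's validity does not depend on it.

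**What to change.** Before unblinding, amend Section V, item 12 as follows.

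- State that the crossover outcome is the post-dose MS-Tls, FC or D.
- Add to the treatment, group and group × treatment model the same-visit pre-dose value of the same measure (same voxel or region and, for D, same threshold), centred within subject. A single baseline or a subject average would not do, because it cancels out of the treatment contrasts.
- Name morphine–placebo and naltrexone–placebo as the planned contrasts.
- State the assumption that earlier doses do not shift later pre-dose scans. Check it by comparing pre-dose values by previous treatment, as an aid to interpretation and not as a rule for choosing the analysis.
- Report the unadjusted post-dose analysis as a sensitivity analysis.

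Milkshake ratings should be adjusted in the same way only if they are also collected before the dose, which the Day 3 procedure does not say.

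The cost is one residual degree of freedom (116 to 115 with 60 participants), processing of pre-dose scans already acquired, a voxel-specific covariate in the whole-brain models, and the added carryover assumption. No new scans or participants are needed.

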1. Alternatives: What other alternatives are available to the study subjects outside of the research?

The healthy participants for this study are not in need of treatment or seeking treatment. For this reason there is no alternative, except to decline participation in the study. The pain participants might feel short-term relief of pain; If patients are interested in seeking such treatment they will be asked to talk to their doctor about it.

2. **Payments for Participation (Economic Considerations):** Describe any payments that will be made to subjects, the amount and schedule of payments, and the conditions for receiving this compensation. The subject's payments for the open label and the randomized controlled study are the same per session completed.

Remuneration is as follows for the randomized controlled study:

Type session:	payment:	frequency	Total
behavioral assessment	\$ 80	x 1	= \$80
fMRI scan with milkshake	\$ 100 *	x 3	= \$ 300
Computer Games	\$100	x 1	= 100
-		Subtotal:	$= \frac{380}{380}$
Completion Bonus	\$ 50	x 1	$=$ $\frac{50}{50}$
Accumulated Earnings Bonus		x 1	$=$ $\sqrt[6]{Variable}$
ç		Total payment:	= \$ 530

And for the open label study:

Type session:	payment:	frequency	Total
behavioral assessment	\$ 80	x 1	= \$ 80
fMRI scan with milkshake	\$ 100 *	x 2	= \$ 200
Computer Games	\$100	X	= \$100
		Subtotal:	= \$ 280
Accumulated Earning Bonus	\$		= \$ variable
Completion Bonus	\$ 50		= \$ 50

Total payment: = \$ 430

NCT04342130

* If the subject spends up to 15 minutes in the scanner but do not complete the study, they will instead be paid \$50. If the subject spends more than 15 minutes, they will receive the full \$100 regardless of study completion.

Subjects will participate in one Intake Session (\$80), 3 fMRI scanning sessions (with milkshake, each \$100), and a completion bonus of \$50, leading to a maximal remuneration of \$430. In addition to this, they make variable earnings depending on their performance on one of the computer tasks.

3. **Costs for Participation (Economic Considerations):** Clearly describe the subject's costs associated with participation in the research, and the interventions or procedures of the study that will be provided at no cost to subjects.

There are no costs to the subject.

- 4. In Case of Injury: This section is required for any research involving more than minimal risk.

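### A visit term and use of all available visits would cheaply protect the power of the three-visit crossover analysis

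*Combined protocol and SAP*

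**What the plan says.** Section V.12 (Statistical Considerations) is the only statement of the group analysis. It describes a within-participant design "with treatment (Morphine, Naltrexone and Placebo) being the repeated measure and groups (healthy control vs. pain patients) as a factor" and continues "We will use repeated measures ANOVA to find differences in brain response" and in milkshake ratings. The brain measures are the milkshake-minus-tasteless parameter estimate (MS-Tls), degree (D) and functional connectivity (FC). The section defends the design on efficiency: "The repeated measures design is a powerful one".

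Section V.3, Day 3 step 5, gives the visit structure. Participants are scanned, dosed, and 60 minutes later "participants will undergo another scanning session while receiving milkshake, sucrose or tasteless solutions". This is repeated on Days 4 and 5. The "visits will be scheduled within a period spanning 4 weeks", with dosing days at least 48 hours apart. On sequence: "However, the order of the interventions (i.e. Morphine, Naltrexone or placebo) will be randomized". Balancing of the drug orders is not mentioned; the counterbalancing in that section concerns taste blocks.

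Incomplete participation is foreseen. Section X.2 sets a reduced payment: "If the subject spends up to 15 minutes in the scanner but do not complete the study, they will instead be paid" half the scan fee. Section VII allows withdrawal at any time. The opening steps of the Day 3 session cancel on positive tests or low vital signs. No section says how a participant with one or two usable visits is analysed.

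**The concern.** A three-visit crossover has three sources of variation that the model can remove: participant, treatment and visit. The plan removes the first two. If responses drift over visits, for example through habituation to the scanner or the tastes, that drift stays in the error term of every drug contrast.

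Repeated measures ANOVA is also commonly run on complete sets only. If so here, a participant who misses just the naltrexone visit would lose a valid morphine-placebo pair. The plan's one argument for the design is its power, and both features could erode it.

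A prior gap affects the size of the problem. Each visit yields a pre-dose and a post-dose scan, and Section V.12 does not say whether the outcome is the post-dose value or the change.

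**Working it through.** **Inputs from the documents.** Three visits, randomised order (V.3). Model terms treatment and group (V.12). Enrolment target 75 (VII.1); 15 open-label patients (V.3.B). If the 15 are within the 75, the crossover has 75 - 15 = 60. The plan states no power, effect size, SD, drift or loss rate, so there is no figure of its own to reproduce.

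**Assumptions.** n = 60 in two equal groups; one ROI- or rating-level morphine-placebo contrast; two-sided 5%; effect 0.5 within-participant SD; simple randomisation over the six orders; drift of b SD per visit.

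**1. Drift, post-dose outcome, complete data.** Over the six orders the morphine-placebo position difference is ±1 in four and ±2 in two, so its variance is (4×1 + 2×4)/6 = 2. Without a visit term, the per-participant contrast variance rises from 2s² to 2s² + 2b²s², a factor of 1 + b². The noncentrality is 0.5 × √(60 / [2(1 + b²)]). Error df are 180 - 60 - 4 = 116, critical t 1.981.
- b = 0: noncentrality 2.739, power 77.5%.
- b = 0.25: factor 1.0625, noncentrality 2.657, power 75.0%.
- b = 0.5: factor 1.25, noncentrality 2.449, power 68.1%.

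Paired simulation (20,000 runs) agrees and adds the model with visit:

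| Drift per visit (SD) | No visit term | Visit term | Gain |
|---|---|---|---|
| 0 | 77.6% | 76.9% | -0.7 |
| 0.125 | 76.8% | 76.8% | 0 |
| 0.25 | 75.1% | 76.6% | +1.5 |
| 0.375 | 71.9% | 76.6% | +4.7 |
| 0.5 | 67.4% | 76.4% | +9.0 |

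Separate simulations of the 0.25 SD case gave gains of up to about 2 points.

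**2. Missing visits spread evenly over drugs, no drift.** At 10% loss per visit, complete sets are 0.9³ = 0.729 (about 44 of 60), while morphine-placebo pairs are 0.9² = 0.81 (about 49 of 60). Complete-case ANOVA against a mixed model with visit on all visits (between-participant SD set equal to within-participant SD):
- 2% loss: 74.5% vs 75.4% (+0.9).
- 5% loss: 70.5% vs 73.9% (about +3).
- 10% loss: 63.6% vs 71.3% (+7.7; +6.6 with participant as a fixed effect).
- Permanent dropout of 10% after each visit: 68.2% vs 70.8% (+2.6).

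In the even 10% case the loss without the change is 77.6 - 63.6 = 14.0 points, and 7.7/14.0 = 55% of it is regained.

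**3. Loss confined to morphine visits, no drift.** These participants have no morphine-placebo pair to rescue, so the gain is smaller:
- 10% of morphine visits: 72.2% vs 73.3-73.4%.
- 20%: 67.6% vs 69.5-70.1%.
- 30% (as many lost scans as 10% of all visits): 61.5% vs 64.1-65.5%.

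Across independent simulations the gain ran from about +0.4 to +4.

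**4. Post-minus-pre outcome.** Additive drift cancels. At pre-post correlations of 0.3, 0.5 and 0.7, complete data without and with the visit term give 64.5 vs 63.6, 77.8 vs 77.2 and 94.1 vs 93.8, a cost under 1 point. At 10% even loss, complete-case against all visits gives 49.2 vs 54.3, 63.3 vs 68.8 and 83.6 vs 88.6, a gain of about 5 points.

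**5. Validity.** Type I error was 4.9-5.2% for the ANOVA and 4.8-5.2% for the mixed model, at b = 0 and 0.5 with 0 and 10% loss.

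**6. Cost with neither problem.** Error df fall from 116 to 114, which alone is negligible. Most of the cost is chance imbalance of orders over visits; with balanced orders at n = 60 it is about zero. Under simple randomisation it is 0.5-0.8 points at 60, 0.4-0.6 at 75, 1.1-1.6 at 30 and 1.3-2.0 at 24.

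**The case against.** The strongest reply is that the benefit rests wholly on inputs the documents do not give. Most of this stands.

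- **Drift may already cancel.** With a pre-dose scan at every visit, change from pre-dose is a natural outcome, and the visit term then gains nothing against additive drift. MS-Tls is a within-session difference, so session shifts common to both tastes cancel there too. D, FC, ratings and taste-specific change stay exposed. The mock-scanner run at intake may also reduce first-visit novelty. No section reports drift.
- **Complete-case deletion is not stated.** A reader might infer it from the method's name; it is usual, but the text does not commit to it.
- **Even loss is a favourable case.** Section VI lists drowsiness, nausea and vomiting for morphine, and the post-dose scan requires swallowing while supine. Loss concentrated on morphine visits is plausible, and the gain is then small. The four-week window also leaves room to rebook.
- **The crossover may be smaller than 60.** Consent precedes screening, so enrolled participants may not all be scanned, and the cost then approaches 1 to 2 points.
- **Voxelwise maps.** The figures are for a single contrast and do not transfer directly.

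These points limit the size. They do not supply the missing visit term or the missing rule, and they do not make the change costly.

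**Conclusion.** The concern holds as a cheap improvement in efficiency. The stated model leaves visit out of a randomised-order three-visit crossover and has no rule for incomplete sets. At the assumed n = 60 and effect of 0.5 SD, the consequence runs from a small saving (no drift, no loss) to about 9 points of power lost to drift of 0.5 SD per visit on a post-dose outcome. Separately, 6 to 8 recoverable points are lost if 10% of visits go missing evenly and incomplete participants are dropped. Break-even for the visit term is drift of about 0.125 SD per visit.

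Three stronger readings are not supported. The omission does not bias drug contrasts or inflate false positives, because order is randomised. Using all visits does not avoid the loss from missing scans: it regains about half under even loss, less under morphine-only loss, and nothing for participants removed entirely. Nor is the whole Day 3 cancellation text unclear. The low-vital-signs sentence excludes the participant, and the opiate or methadone sentence disqualifies the subject. Only the general positive-test sentence, which cancels the study without saying whether the visit or the participant is lost, is open.

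**What to change.** In Section V.12:

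1. State whether each outcome is the post-dose value or post-minus-pre.
2. For each ROI- or rating-level outcome (MS-Tls, D, FC, milkshake rating), use a linear mixed model with fixed effects for treatment, visit (1 to 3), group and treatment × group, a random participant effect, and all available visits.
3. Put the same visit covariate in the voxelwise model.

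In Section V.3, reconcile the general positive-test sentence with those that exclude or disqualify the participant, so that the analysis set is defined. This point takes no position on what the rule should be.

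The cost is analysis wording, two error degrees of freedom, and about 1 point of power or less on complete data at 60 to 75 crossover participants (up to 1.2 with 10% visit loss; about 1 to 2 at 24 to 30). Using all visits assumes they are missing at random, and the random participant effect assumes equal variances across drugs, as the planned ANOVA does. No extra participants or visits are needed.
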